2.1.3.3 Other efficacy endpoint(s)

Other efficacy endpoints (sotagliflozin 400 mg and 200 mg doses):

- Change from Baseline to Weeks 26 and 52 in FPG.
- Number of hospital visits due to hypoglycemia during the 52-week Treatment Period.
- Change from Baseline in eGFR.
- Change from Baseline to Weeks 26 and 52 in SBP for all patients and the subset with baseline SBP \geq 130 mmHg.
- Change from Baseline to Weeks 12, 26, and 52 in SBP for patients with baseline SBP $<$ 130 mmHg.
- Change from Baseline to Weeks 12, 26, and 52 in DBP for all patients and the subset with baseline DBP \geq 80 mmHg.
- Proportion of patients requiring rescue treatment for hyperglycemia during the 52-week Treatment Period.
- The proportion of patients with HbA1c $<$ 6.5%, $<$ 7.0% at Week 52.
- The proportion of patients with HbA1c $<$ 6.5%, $<$ 7.0% at Week 52 and no documented symptomatic hypoglycemic event (\leq 70 mg/dL) during the 52-week Treatment Period.
- PQAT at Weeks 26 and 52.

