The categorical secondary efficacy variables of HbA1c $< 6.5\%$, $< 7\%$ at Week 52 will be analyzed respectively using a Cochran-Mantel-Haenszel (CMH) method stratified by randomization stratum of HbA1c ($\leq 8.5\%$, $> 8.5\%$), and randomization stratum of SBP (< 130 mmHg, ≥ 130 mmHg). The proportion in each treatment group will be provided, as well as the difference of proportions between sotagliflozin 400 mg and placebo with associated 2-sided 95% CI. For HbA1c responders at Week 52 ($< 6.5\%$, $< 7\%$ respectively), all values at Week 52 will be used to determine whether a patient is a responder or not, even if they are measured after IMP discontinuation or rescue medication use. Patients who have no HbA1c measurement at Week 26 will be treated as non-responders. Summary tables and graphs will also be provided by treatment group at scheduled visits. For between-group comparison, a sensitivity analysis will be performed respectively for HbA1c $< 6.5\%$ responder analysis by excluding patients whose HbA1c values at baseline are $< 6.5\%$, and for HbA1c $< 7\%$ responder analysis by excluding patients whose HbA1c values at baseline are $< 7\%$ using the same CMH test mentioned above. Similarly, by-visit summary may also be provided excluding those patients.

The categorical secondary endpoint, the proportion of patients with at least one documented symptomatic hypoglycemic event (≤ 3.9 mmol/L [≤ 70 mg/dL]) during the 52-week Treatment Period, will be analyzed respectively using a Cochran-Mantel-Haenszel (CMH) method stratified by randomization stratum of Screening HbA1c ($\leq 8.5\%$, $> 8.5\%$) and randomization stratum of Screening SBP (< 130 mmHg, ≥ 130 mmHg). The proportion in each treatment group will be provided, as well as the difference of proportions between sotagliflozin 400 mg group and glimepiride group with its associated 2-sided 95% CI. Summary tables and graphs will also be provided by treatment group at scheduled visits.

Sensitivity analyses

Tipping-point analysis similar to that is described in [Section 2.4.4.1](#) will be performed to evaluate the robustness of the treatment effect on HbA1c data for the following comparisons, using the same MI method and similar ANCOVA model for the primary endpoint analysis:

- Superiority comparison of sotagliflozin 400 mg and placebo on change from Baseline to Week 26.
- Superiority comparison of sotagliflozin 200 mg and placebo on change from Baseline to Week 26.

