2.4.4.3 Analysis of other efficacy endpoints

The analysis of other endpoints (see [Section 2.1.3.3](#)) will be descriptive with no formal testing. Summary statistics at scheduled visits based on observed value will be provided by each treatment group. Graphical presentations will also be used to illustrate trends over time as appropriate.

Hospital visits due to hypoglycemia includes emergency room visit, outpatient visit and any hospitalization due to hypoglycemia. It is identified in e-CRF “Hypoglycemic Event” page as those documented as ticked “Yes” to the question “As a result of this hypoglycemia event, did a hospital visit occur?” The number (%) of patients with hospital visits due to hypoglycemia will be provided by each treatment group during the TEAE period defined for hypoglycemia, as well as the incidence rate in patient years if any patients have multiple hospital visits due to hypoglycemia. The number (%) of patients who used rescue therapy and a KM curve for the time-to-first rescue therapy will be provided by treatment group. A list of patients who used rescue therapy will also be provided (see [Section 2.5.4](#)).

For the categorical endpoints of HbA1c responders (<6.5% and <7%, respectively) and HbA1c responders with no hypoglycemic event, summary tables and graphs will be provided by each treatment group at scheduled visits. All values will be used to determine whether a patient is a responder or not at each visit, even if they are measured after IMP discontinuation or rescue medication use. Patients who have no HbA1c measurement at each scheduled visit will be treated as non-responders. For the composite endpoint of HbA1c responders and no documented symptomatic hypoglycemic event, a patient will be treated as a responder only if the criterion is met for each component.

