2.5.2 Data handling conventions for secondary efficacy variables

Scheduled measurements (see [Section 2.5.4](#)) of continuous efficacy variables collected during the study will be used in the analyses including those obtained after IMP discontinuation or introduction of rescue therapy. Continuous secondary efficacy endpoints will be analyzed with missing values imputed by the retrieved dropouts MI method (if there are at least 5 patients in each study treatment group who discontinued but have the endpoint) or washout MI method according to the criterion described in [Section 2.4.4.1](#).

For the categorical secondary efficacy endpoints, data handling conventions are described in [Section 2.4.4.2](#).

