2.5.3 Missing data

For categorical variables, patients with missing data are not included in calculations of percentages unless otherwise specified. When relevant, the number of patients with missing data is presented.

Derived variables will be considered missing if any of the original variables required to calculate them are missing. For example, if either a baseline assessment or an endpoint assessment is missing for a particular patient, then change from baseline at endpoint will be missing. Depending upon the assessment, analyses may not include all patients in the analysis population, because certain patients in the intended population may have missing data.

Incomplete date of first administration of double-blind IMP

Date/time of first administration is the first non-missing start date/time of double-blind IMP completed in the e-CRF “First dose IMP” module.

For patients who are randomized and dispensed a double-blind treatment kit but who are lost to follow-up just after Visit 3 (eg, only the treatment kit number is reported in the e-CRF “Exposure - Treatment Period (Capsule)” or “Exposure - Treatment Period (Tablet)” module without any dose information), the date of first administration will be imputed using the date of randomization. When a patient is randomized but not exposed, “Not taken” should be ticked for both Capsule and Tablet in the e-CRF “First dose IMP” module.

Handling of computation of treatment duration if IMP end of treatment date is missing

For the calculation of the treatment duration, the date of the last dose of double-blind IMP is equal to the date of last administration reported on the e-CRF “Treatment Status Library” page. If this date is missing, the exposure duration should be left as missing.

The last dose intake should be clearly identified in the case report form and should not be approximated by the last returned package date.

Handling of medication missing/partial dates

No imputation of medication start/end dates or times will be performed. If a medication date or time is missing or partially missing and it cannot be determined whether it was taken prior or concomitantly, it will be considered a prior, concomitant, and posttreatment medication.

Handling of adverse events/hypoglycemia with missing or partial date/time of onset

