If the assessment of the relationship to glimepiride or matching placebo (Capsule) is missing, then the relationship to Capsule has to be assumed and the AE considered as such in the frequency tables of possibly Capsule-related AEs. If the assessment of the relationship to sotagliflozin or matching placebo (Tablet) is missing, then the relationship to Tablet has to be assumed and the AE considered as such in the frequency tables of possibly Tablet-related AEs. No imputation should be done at the data level.

Handling of missing severity/grades of adverse events

If the severity/grade is missing for one of the treatment-emergent occurrences of an AE, the maximal severity on the remaining occurrences will be considered. If the severity is missing for all the occurrences, a “missing” category will be added in the summary table.

Handling of potentially clinically significant abnormalities

If a patient has a missing baseline he will be grouped in the category “normal/missing at baseline.”

For PCSAs with two conditions, one based on a change from baseline value or a normal range and the other on a threshold value, with the first condition being missing, the PCSA will be based only on the second condition.

For a PCSA defined on a threshold and/or a normal range, this PCSA will be derived using this threshold if the normal range is missing; eg, for eosinophils the PCSA is >0.5 GIGA/L or $>ULN$ if $ULN \geq 0.5$ GIGA/L. When ULN is missing, the value 0.5 should be used.

Measurements flagged as invalid by the laboratory will not be summarized or taken into account in the computation of PCSA values.

Linked adverse events that worsened or became serious

An AE that worsened or became serious will have a separate record in the data from the original event record with an AE identification number that links the new record to the original record. An AE that worsened or became serious will be considered a new recurring AE in the summary of recurrent events or in the summary of events by time intervals.

Handling of missing data for continuous efficacy endpoints

Please see [Section 2.4.4.1](#) and [Section 2.4.4.2](#).

Handling of missing data for categorical secondary efficacy endpoints

Please see [Section 2.4.4.2](#).

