2.5.4 Windows for time points

The following steps will decide how the scheduled and/or unscheduled visits will be used in the analyses on efficacy variables and the by-visit summaries for safety variables (clinical laboratory data in [Section 2.1.4.4](#) and vital signs in [Section 2.1.4.5](#)).

Step 1: A scheduled measurement will be used if it is available; otherwise, an unscheduled measurement (including the end of treatment/study visit for those prematurely discontinued) will be used if it happens to be on the same date as the date of the scheduled visit.

Step 2: After Step 1, if there is still no measurement for a given parameter at a scheduled visit, the analysis window below ([Table 4](#)) will be applied to re-allocate a postbaseline unscheduled measurement to a scheduled measurement.

Table 4 - Analyses window definition

Scheduled visit post baseline	Targeted study day	Analysis window in study days
Week 2 (V s t 4)	14	2 to 20
Week 4 (V s t 5)	28	21 to 41
Week 8 (V s t 6)	56	42 to 69
Week 12 (V s t 7)	84	70 to 104
Week 18 (V s t 9)	126	105 to 153

COVANCE INC. CONFIDENTIAL

Scheduled visit post baseline	Targeted study day	Analysis window in study days
Week 26 (V s t 10)	182	154 to 227
Week 39 (V s t 11)	273	228 to 318
Week 52 (V s t 12)	364	≥319

Study days are calculated from the day of first administration of double-blind MP (or the day of randomization if not exposed) is Day 1

After applying the above time windows, if multiple assessments are associated to the same time point, the closest from the targeted study day will be used. In case of equality, the last measurement will be used. Re-allocated scheduled visits (ie, visit numbers) should be sequential if ordered by the date of measurement.

After Step 2, if there is still no measurement for a given parameter at a scheduled visit, data are considered missing for efficacy analyses, where MI would be applied as appropriately as described in [Section 2.4.4](#).

Reference day

The reference day for the calculation of extent of exposure, time to onset, and relative days will be the day of the first administration of double-blind IMP or the day of randomization if not exposed to double-blind IMP, denoted as Day 1.

Baseline definition for efficacy/safety data

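### SAP 2.4.4.2 keys the non-responder rule for Week 52 HbA1c response to Week 26, and its completers analysis pairs a 26-week period with a comparison defined only at Week 52

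*SAP*

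**What the plan says.** **Responder rule.** SAP 2.4.4.2 sets out the <6.5% and <7% HbA1c responder analyses at Week 52 and says "all values at Week 52 will be used to determine whether a patient is a responder or not", including values after IMP discontinuation or rescue. The next sentence reads "Patients who have no HbA1c measurement at Week 26 will be treated as non-responders". For the same endpoints, SAP 2.4.4.3 says "Patients who have no HbA1c measurement at each scheduled visit will be treated as non-responders".

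**Routing and classification.** SAP 2.4.4.2 calls these variables categorical secondary and plans a stratified CMH comparison of 400 mg with placebo. SAP 2.1.3.3, SAP 2.4.4.3 and Appendix D place them among the other endpoints, with no formal testing. SAP 2.5.2 states "For the categorical secondary efficacy endpoints, data handling conventions are described in" Section 2.4.4.2. SAP 2.5.3 gives the same reference under "Handling of missing data for categorical secondary efficacy endpoints". SAP 2.5.3 also sets a default for categorical variables: "patients with missing data are not included in calculations of percentages unless otherwise specified".

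**Completers analysis.** The sensitivity paragraph of SAP 2.4.4.2 takes patients who complete a double-blind treatment period of 26 weeks without rescue. It uses them for non-inferiority of 400 mg versus glimepiride on HbA1c, with the ANCOVA model of 2.4.4.1 and washout imputation. It names no analysis visit.

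**The concern.** Two adjacent sentences classify the same patient differently. A patient below the threshold at Week 52 with no Week 26 sample is a responder by the first and a non-responder by the second. A patient with a Week 26 value but no Week 52 value is not covered in that section at all. Programmers working from 2.4.4.2 and from 2.4.4.3 could report different Week 52 responder rates, each with support in the text.

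The completers paragraph leaves a similar choice open. Its period matches neither the treatment period nor the defined completers population, and the comparison it names is hypothesised only at Week 52. The population and the visit therefore have to be guessed.

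**Working it through.** **Responder rule.** The documents give no response or missingness rates for this endpoint, so every rate below is an assumption. Let p be the response rate among patients with a Week 52 value, taken as the same whether or not Week 26 is present. Let a be the share missing Week 26 only, b the share missing Week 52 only, and c the share missing both.

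1. Corrected rule (missing Week 52 means non-responder): rate = p(1 − b − c).
2. Sentence as written, with 2.4.4.3 covering missing Week 52: rate = p(1 − a − b − c). The change from step 1 is −p·a.
   - p = 0.40: a = 1%, 3%, 5% gives −0.4, −1.2, −2.0 points. On 310 patients that is 1.2, 3.7 and 6.2 patients.
   - Wider range: p = 0.20, a = 1% gives −0.2; p = 0.60, a = 5% gives −3.0 points.
3. Sentence as written, with the 2.5.3 exclusion default for patients missing Week 52 only: rate = p(1 − a − b − c)/(1 − b).
   - p = 0.40, a = 1%, b = 20%, c = 10%: 0.40 × 0.69/0.80 = 34.5%. The corrected rule gives 0.40 × 0.70 = 28%.
   - Step 3 exceeds step 1 whenever a < b(1 − b − c). Here 1% < 0.20 × 0.70 = 14%.
4. Shift in the 400 mg minus placebo difference under step 2, with assumed response of 40% and 20%: −(0.40·aT − 0.20·aP), where aT and aP are the shares missing Week 26 only on 400 mg and placebo.
   - aT = 5%, aP = 1%: −1.8 points. aT = aP = 1%: −0.2. aT = aP = 5%: −1.0. aT = 1%, aP = 5%: +0.6.
   - Standard error = √(0.40 × 0.60/310 + 0.20 × 0.80/155) = 4.25 points.

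The share a is likely to be small. Under SAP 2.5.4 the analysis window "will be applied to re-allocate a postbaseline unscheduled measurement to a scheduled measurement", and for Week 26 it runs from Day 154 to Day 227.

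**Completers analysis.** The nearest figure in the plan is 80% power for Week 52 completers with 30% dropout (SAP 1.3). It reproduces: 310 × 0.70 = 217 per arm; 0.3/(1.1 × √(2/217)) = 2.84; 2.84 − 1.96 = 0.88, which gives 81.1%.

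The relevant texts compare as follows:
- SAP 1.1: the double-blind period is 52 weeks.
- SAP 2.3.1.2: completers finish 52 weeks and do not start rescue.
- SAP 2.4.4.1, sensitivity analyses: 52-week completers, Week 52 values.
- SAP 2.4.4.1 and 2.4.4.4: non-inferiority of 400 mg to glimepiride is hypothesised at Week 52 only. The Week 26 HbA1c hypotheses are superiority to placebo.
- Appendix D, secondary row: completers are tied to HbA1c change to Week 52.
- SAP 2.4.4.2, its own list of four HbA1c comparisons: the only non-inferiority entry is 200 mg at Week 52.

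For set size only: 310 × 0.30 = 93 dropouts per arm. If 30% to 70% of them leave after Week 26 (assumption), a 26-week set has 217 + 0.3 × 93 = 245 to 217 + 0.7 × 93 = 282 per arm, against 217. All three are upper figures, because patients who start rescue are also excluded. The effect on the estimate cannot be quantified without a visit.

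**The case against.** **The intended responder rule is already in the SAP.** The formal list of secondary endpoints (SAP 2.1.3.2) has one categorical item, hypoglycaemia. HbA1c response is listed as an other endpoint there and in Protocol 9.1.4. On that classification 2.4.4.3 governs, and the references in 2.5.2 and 2.5.3 do not send the reader to the faulty sentence. This stands as evidence of intent. It does not remove the conflict, because 2.4.4.2 itself calls these variables secondary and states its own operative rule.

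**The completers paragraph can be read coherently.** It borrows the 2.4.4.1 model, which for HbA1c is at Week 52, and it imputes missing endpoint data. It could therefore mean 26-week completers analysed at Week 52 with later gaps imputed. This stands as one possible reading. The paragraph does not state it, and it departs from the defined completers population.

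**Stronger readings that the documents do not support:**
- A reader might infer that the sentence as written always understates response. Step 3 of the working shows it can overstate it.
- A reader might infer that the secondary Week 52 comparisons (200 mg non-inferiority and 400 mg superiority versus glimepiride) have no completers analysis. SAP 2.4.4.2 applies the 2.4.4.1 tipping-point method to both, and 2.4.4.1 runs that method on completers as well as ITT.
- A reader might infer that the CMH comparison breaches error control. SAP 2.4.4.4 leaves it outside the controlled sequence, so the inconsistency is one of labelling.

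**Conclusion.** The responder sentence is wrong as written: it contradicts the sentence before it and SAP 2.4.4.3. Under the stated assumptions it lowers a rate by 0.4 to 2.0 points if 2.4.4.3 covers missing Week 52 values. It can raise the rate by several points if the 2.5.3 default is applied. Under the first handling, the between-arm shift (−1.8 to +0.6 points) is well inside one standard error.

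The completers paragraph is inconsistent with the rest of the SAP, but the documents do not show whether the period or the comparison is the error, or whether a hybrid analysis was meant. It would be too strong to call 26 weeks a plain slip for 52.

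Severity is minor. The primary analysis, the fixed sequence, the sample size and the 52-week completers analysis in 2.4.4.1 are untouched. Confidence is high that both inconsistencies exist. The size of the effect rests on assumed rates.

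**What to change.** 1. In the non-responder sentence of SAP 2.4.4.2, change Week 26 to Week 52, so that it agrees with 2.4.4.3.
2. Classify the HbA1c responder endpoints the same way in 2.1.3.3, 2.4.4.2, 2.4.4.3 and Appendix D. State whether the CMH comparison with placebo is kept and, if so, that it lies outside the testing sequence.
3. Reconcile the completers paragraph in 2.4.4.2 with 2.3.1.2, 2.4.4.1 and Appendix D by naming its population, visit and comparison. If it means 52-week completers at Week 52 for 400 mg non-inferiority, it repeats the analysis in 2.4.4.1 and could say so.

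The cost is SAP wording, plus a rerun of the responder tables if they were programmed from the sentence as written. Reported rates could then move either way. SAP section 4 records database lock on 12Sep2019, before version 3 (03-Apr-2020), so the changes should be logged in SAP Table 2. Item 1 adds no new rule, because 2.4.4.3 already contains it.
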